Growing evidence indicates that vitamin D's effect on reducing falls is mediated by improvements in neuromuscular function.⁶⁻⁸ We and others have shown associations between 25(OH)D concentrations and muscle strength and physical performance measures associated with fall risk (e.g., gait, balance) in observational studies.^{6,9-13} Yet trials of vitamin D supplementation on changes in muscle strength and physical performance are equivocal,¹⁴ likely due to inadequate trial duration, small sample sizes, insufficient vitamin D dose, and sample heterogeneity. Moreover, vitamin D's effects on the mechanisms underlying neuromuscular function are not well understood. Determining whether increasing 25(OH)D concentrations to ≥ 30 ng/mL will improve neuromuscular deficits that are risk factors for falls and elucidating the underlying physiological mechanisms linking vitamin D and neuromuscular function could change clinical practice by providing evidence to guide vitamin D supplementation recommendations for neuromuscular-related outcomes in older adults.

Objectives

To conduct a 12-month, double-blind randomized placebo controlled trial in 136 older (65-89 yrs) men and women with initial 25(OH)D concentrations of 18- <30 ng/mL to determine the effect of increasing 25(OH)D concentrations to ≥ 30 ng/mL through vitamin D₃ supplementation on 1) change in neuromuscular functions that are established risk-factors for falls in older adults; and 2) changes in the underlying physiological mechanisms over 4 months in a subset of 36 randomly selected participants. Participants will be randomized to 2000 IU/d of vitamin D₃ (a dose expected to increase 25(OH)D concentrations by ~ 14 ng/mL) or placebo.

Hypothesis 1: Compared to participants randomized to placebo, participants randomized to vitamin D₃ will have increased lower extremity muscle power and strength, increased physical performance, decreased postural sway, and reduced rate of falls over 12 months.

Hypothesis 2: Compared to participants randomized to placebo, participants randomized to vitamin D₃ will have increased type II muscle fibers, muscle fiber force, and myofiber regeneration, and decreased muscle fiber denervation over 4 months.

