Lower extremity muscle strength and power, physical performance, and postural sway will be assessed at baseline, 4 months and 12 months and falls assessed monthly. Muscle biopsies of the *vastus lateralis* will be taken at baseline and 4 months to assess muscle fiber type, contractility, and denervation, and number and differentiation stage of satellite cells. The primary outcomes are change in lower extremity muscle power (Hypothesis 1) and change in percentage of type II (fast-twitch) muscle fibers (Hypothesis 2). Secondary outcomes include change in lower extremity muscle strength, physical performance, and postural sway (Hypothesis 1) and muscle fiber contractility, muscle fiber denervation, and number and differentiation of satellite cells (Hypothesis 2). Falls will also be assessed as an exploratory outcome (Hypothesis 1).

Methods and Measures

Experimental Overview/Study Design

This study is a 12-month, double-blind randomized placebo controlled trial in 136 older (65-89 yrs) men and women with initial 25(OH)D concentrations of 18-<30 ng/mL to determine the effect of increasing 25(OH)D concentrations to ≥ 30 ng/mL through vitamin D₃ supplementation on 1) change in neuromuscular functions that are established risk-factors for falls in older adults and 2) changes in the underlying physiological mechanisms over 4 months in a subset of 36 randomly selected participants. Participants will be randomized to vitamin D₃ (2000 IU/d) or matching placebo in a 1:1 ratio stratified by gender and race.

Recruitment of study participants

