Muscle biopsies: Muscle will be obtained in a stratified sample of participants from the *vastus lateralis* using the percutaneous needle biopsy technique.¹⁸ The *vastus lateralis* is a good representative muscle for the *in vitro* study of skeletal muscle in older persons.¹⁹ By conducting an average of 3-4 passes (some may require additional passes depending on body composition) from a single incision, tissue samples of an average of 500mg (more or less depending on body composition) are obtained, which is sufficient for the mechanistic analyses proposed and any remaining tissue will be frozen and stored for future use. Up to 40 participants may be approached for a baseline muscle biopsy to ensure that at least 32 participants complete the 4-month muscle biopsy and allow for biopsy samples that yield insufficient muscle for analyses. Once the specimen is obtained, visible blood and connective tissue is removed, and portions for specific assays are partitioned. A portion for histochemical analysis (\geq 20 mg) will be oriented such that the fibers run longitudinally, mounted in a histology tray in embedding medium (OCT compound, Miles Laboratory, Naperville, IL), and frozen in isopentane cooled to its freezing point with liquid nitrogen. Another portion to be used for RNA extraction (\geq 50 mg) will be snap frozen in liquid nitrogen (within 30 seconds of the biopsy) and stored at -80°C until analyses. A portion of muscle tissue will be homogenized for extraction of mitochondria (\geq 50 mg).

Vitamin D intervention

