Type I and type II denervated myofibers will be identified using ATPase pH 9 plus NCAM immunostaining analysis. The whole muscle biopsy will be cryosectioned and 10-12 slices will be mounted per slide. Alternate slides will be stained for NCAM and positive fibers and their expression pattern (perimeter or whole cross section) will be reported as a percent of the total number of fibers. Additionally, fiber grouping (the area occupied by at least two contiguous fibers expressing a predominantly similar myosin heavy chain isoform – type I or II, fully surrounded by fibers of the same predominant myosin heavy chain), a classical evidence of a neurogenic process, will be examined. NCAM+ number and density (NCAM+ number per cross sectional area) and fiber grouping (%) by fiber type (I or II) at baseline and 4-month follow-up will be used in analysis.

Regulation of Runx1 and its dependent genes will be assessed by RNA extraction using the TRIzol method (Invitrogen). Runx1 and its dependent genes will be measured by qRT-PCR and normalized to GAPDH expression. We will use the cycle threshold (CT), defined as the number of cycles required for the fluorescent signal to cross the threshold, as the parameter to calculate $2^{-\Delta\Delta CT}$, which is needed to compare the gene expression in two different samples. Expression of Runx1, Chrny, Scn5a, Myh3, Myog, NCAM1 at baseline and 4-month follow-up will be used in analysis.

Satellite cell differentiation will be assessed in serial muscle cross sections immunostained for Pax7/NCAM satellite cells (SCs). SC number and density (SC per cross sectional area) by fiber type (I or II) at baseline and 4-month follow-up will be used in analysis.

Vitamin D Receptor (VDR) expression will be measured by Western blots using the C20 antibody raised against a peptide mapping at the C terminus of VDR and normalized to actin used as a loading control. VDR concentration at baseline and 4-month follow-up will be used in analysis.

Exploratory outcomes (Wake Forest Pepper Center Pilot; [name], PI)

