Short Physical Performance Battery score ³⁰	2.05	0.92
Timed Up and Go, sec ⁸²	5.40	2.43
20-m Gait Speed, m/sec ³¹	0.15	0.07
Lower extremity muscle strength, Nm ³¹	21.0	9.5
Postural Sway, mm ¹²²		
Mediolateral (ML) displacement	2.7	1.2
Anteroposterior (AP) displacement	3.9	1.8

*SD calculated assuming a correlation of 0.43 between baseline and follow-up measures.

For the muscle biopsy subsample, we have powered on a difference between the two groups of a relative increase in type II fibers of 25% or more. In our preliminary data in older adults with 25(OH)D concentrations <25 ng/mL treated with 2000 IU/d vitamin D₃ plus 1200 mg/d calcium (n=4) or calcium only (n=2), a 1 ng/mL increase in 25(OH)D concentration was associated with a 2.35% relative increase in type II fibers over 4 months. Assuming that 25(OH)D concentrations will increase by an average of 14 ng/mL in the intervention group, we

expect to see a relative increase in type II fibers of approximately 33%. To allow for the possibility that there may be some increase in the control group due to “drop in” by starting vitamin D supplements or changes in physical activity, a 25% difference between the two groups in the relative increase in type II fibers was selected. Two previously published vitamin D supplementation studies observed increases in type II fibers of 31-34%⁴⁸ and 202%.⁴⁹ Thus, the detectable 25% relative increase is in line with independent observations. A sample size of 16 in each group will have 80% power to detect a difference of 25% assuming that the common standard deviation is 23.7 (based on preliminary data of n=17 participants in a behavioral intervention with data on change in type II muscle fibers) using a two group t-test with a 0.05 two-sided significance level. Allowing for 10% drop out, we will inflate the sample size to 18 per group, for a total of 36 participants. However, up to 40 participants may be approached for a baseline muscle biopsy to allow for biopsy samples that yield insufficient muscle for analyses.

Statistical Analyses

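### NCAM+ and satellite-cell outcomes by fiber type lack a same-type fiber denominator, so the planned rise in type II fibers would shift the counts by itself

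*Combined protocol and SAP*

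**What the plan says.** In the combined protocol and SAP, the biopsy paragraphs of Outcome measures each end with the variables that go into analysis.

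- **Denervation:** "NCAM+ number and density (NCAM+ number per cross sectional area) and fiber grouping (%) by fiber type (I or II".
- **Satellite cells:** "SC number and density (SC per cross sectional area) by fiber type (I or II".
- **A further NCAM+ scale:** the denervation paragraph also says that positive fibers "will be reported as a percent of the total number of fibers". This percent is not in the list of analysis variables, and its denominator is fibers of every type.
- **Grouping:** contiguous fibers of one type, "fully surrounded by fibers of the same predominant myosin heavy chain", analysed as a percentage.
- **Model:** the biopsy paragraph of Statistical Analyses compares these measures by ANCOVA and names age, gender and race as adjustments. It has no term for fibers counted, fiber-type share or fiber size.
- **Expected effect:** Hypothesis 2 (Objectives) predicts "increased type II muscle fibers, muscle fiber force, and myofiber regeneration, and decreased muscle fiber denervation over 4 months". The substudy's primary outcome is "change in percentage of type II (fast-twitch) muscle fibers (Hypothesis 2". Under Statistical Power, "we have powered on a difference between the two groups of a relative increase in type II fibers of 25% or more".
- **Tissue:** under Muscle biopsies, "tissue samples of an average of 500mg (more or less depending on body composition) are obtained".

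The fiber-type paragraph of Outcome measures also has the absolute and relative number of each fiber type, and its cross-sectional area, quantified.

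**The concern.** The number of NCAM+ type II fibers in a section is a product: the number of type II fibers present times the fraction of them that is denervated. Hypothesis 2 expects the first factor to rise and the second to fall, in the same biopsies. A count cannot separate the two. The number of satellite cells by type has the same structure: fibers of that type times satellite cells per fiber.

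Success on the substudy's primary outcome would therefore, by arithmetic alone, push the type II NCAM+ count towards more denervation and the type II satellite-cell count towards more regeneration, and would lower the type I counts. Denervation and satellite cells are the named secondary outcomes through which the mechanism is to be read. The plan also enters the biopsy measures as covariates in its mediation analysis, so the distortion would carry over there.

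**Working it through.** **Inputs from the plan.** 25% difference in the relative increase in type II fibers, SD 23.7, 80% power, two-sided 0.05, 16 per group, 10% dropout (Statistical Power).

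**Assumed, because the plan does not give them.** Baseline type II share p of 0.30, 0.40 or 0.50; no change on placebo; the same number of fibers counted at each biopsy; denervated fraction and satellite cells per fiber unchanged.

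**1. The plan's own figure.** A two-sample t-test with effect size 25/23.7 = 1.055 needs 15.13 per group, rounded up to 16; power at 16 is 82.3%. Then 16/0.9 = 17.8, rounded up to 18. The stated sample size is reproduced. No power is stated for the NCAM+, grouping or satellite-cell outcomes.

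**2. Type II counts.** Share goes from p to 1.25p, so the count changes by 1.25p/p = 1.25, a 25% rise in NCAM+ fibers and in satellite cells.

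**3. Type I counts.** The ratio is (1 − 1.25p)/(1 − p).

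| p | Ratio | Change |
|---|---|---|
| 0.30 | 0.625/0.70 = 0.893 | −11% |
| 0.40 | 0.500/0.60 = 0.833 | −17% |
| 0.50 | 0.375/0.50 = 0.750 | −25% |

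**4. Masking.** If the denervated fraction of type II fibers is multiplied by f, the count is multiplied by 1.25f. This is below 1 only when f < 1/1.25 = 0.80. A true fall of up to 20% gives no fall in the count.

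**5. Density.** The plan does not say which cross-sectional area is meant.

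- *Whole-section area, type II share up 25%:* with equal fiber sizes the total area is unchanged, so type II density rises by 1.25. If type II fibers are 60% the size of type I (assumed) and p = 0.50, total area goes from 0.5×0.6 + 0.5 = 0.80 to 0.625×0.6 + 0.375 = 0.75, and density changes by 1.25×0.80/0.75 = 1.33.
- *Own-type area, type II share up 25%:* numerator and denominator both rise by 1.25, so density does not move.
- *Type II fibers 10% larger (assumed), own-type area:* 1/1.1 = 0.909, a 9% fall.
- *Type II fibers 10% larger, whole-section area, equal sizes at baseline:* 1/(1 + 0.1p) = 0.971, 0.962, 0.952, a fall of 3% to 5%.

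**6. Percent of all fibers.** Split by type, it equals share times denervated fraction, so the type II percent again rises by 1.25. Pooled over types with a common denervated fraction r, it is rp + r(1 − p) = r, which does not move with share.

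**7. Same-type denominator.** NCAM+ type II fibers over all type II fibers: 1.25/1.25 = 1.00. Satellite cells per type II fiber: the same. A change in fiber size alone does not move either.

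**8. Grouping.** Fibers were placed at random on a six-neighbor lattice (assumed geometry), counting enclosed fibers that touch another enclosed fiber of the same type. Type II grouping went from 0.05% to 0.40% of all fibers as the share rose from 0.40 to 0.50, and type I grouping from 1.9% to 0.39%. Grouping thus moves with share by its definition, though the type II levels here are small. Uniform growth in fiber size does not move it.

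**The case against.** The strongest reply has five parts.

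- **The percent already in the plan.** Hypothesis 2 speaks of denervation overall, not by type. A pooled percent of all fibers fits that, does not depend on tissue amount, and does not move with share if the types have equal denervation rates. This stands, and is why the fix includes it. But the percent is missing from the analysis variables, and splitting it by type brings the problem back.
- **Satellite-cell number is itself the named outcome.** True, so number should stay in the report. It still cannot alone show regeneration per fiber.
- **The distortion is conditional.** It arises only if treatment changes fiber share or size, and both are analysed in their own right. A shift would be visible, but the plan says nothing about using it to read these outcomes.
- **Tissue amount should balance between arms.** With randomization and blinded assessors, varying yield adds noise, not bias. The 500 mg is also the whole specimen; the histochemistry portion has only a 20 mg minimum.
- **Denominators may not be on the same slides.** Fiber typing, NCAM staining and satellite-cell staining use different or alternate sections, and the plan does not say that every NCAM-negative fiber is typed. This bears on the cost of the fix.

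A reader might infer that grouping is also a raw count, or that fiber size moves every one of these measures. The documents do not support either: grouping is a percentage, and a raw count over a fixed number of fibers is unaffected by size. Nor do they support saying that density must rise with type II share, since with own-type area it would not.

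**Conclusion.** The concern holds for NCAM+ fibers and satellite cells by fiber type. As written, the plan's own target effect would raise type II counts by 25% and lower type I counts by 11% to 25%, with no change in denervation or in satellite cells per fiber, and would hide a true type II denervation fall of up to 20%. Only the 25% comes from the plan. The type I range rests on an assumed baseline share of 30% to 50%, and all the count figures on a fixed number of fibers counted and an unchanged placebo group.

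For density, the firm point is that the area is undefined, and the direction and size of any artifact depend on it. For grouping, the point is one of interpretation: it depends on type share, by an amount that the documents do not allow to be fixed.

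These are secondary outcomes of the substudy. It would be wrong to infer that the primary comparison of percent type II fibers, or its 16 per group, is compromised.

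**What to change.** In the denervation and satellite-cell paragraphs of Outcome measures:

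1. Make the analysis variables, for each fiber type, NCAM+ fibers divided by all fibers of that type counted, and satellite cells per 100 fibers of that type. Set a minimum fiber count per type for a biopsy to contribute.
2. Add the pooled NCAM+ percent of all fibers, which is already to be reported, to the list of analysis variables.
3. State whether the area used for density is the whole section or the area of that fiber type. Keep number and density as supporting results.
4. Interpret grouping alongside type share, for example against the level expected by chance at the observed share. State what the percentage is a percentage of.

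**Cost.** Mainly wording. Fibers are already to be typed and counted, so no new tissue is needed, but the plan should state which sections supply the denominators and that fibers there are typed whether or not they stain for NCAM. The downside is noisier fractions where few fibers of a type are present, hence the minimum count. Sample size does not change.

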We will examine the distributions of all continuous outcomes of interest, and will transform them to approximate normality if the outcomes show a strong departure from normality as evidenced by examining Q-Q plots and performing the Shapiro-Wilk test. Outliers will be examined on the chosen scale (original or transformed) and may be set to missing if they are 3 or more interquartile ranges above the 75th percentile or below the 25th percentile. Plausible biologic values may be retained even if they are outliers. Implausible biologic values may be set to missing based on a review of health-related events (e.g., AEs related to pain, fractures, surgery) in the interval surrounding the collection of the measurements.

The primary outcome for this trial will be the 12-month measure of muscle power. For the muscle biopsy substudy, the primary outcome will be the change in type II muscle fibers over 4-months. Our primary statistical analyses will proceed on the “intent-to-treat” principle in which data from all randomized participants are used to test the primary hypotheses that compared to placebo, vitamin D₃ supplementation will result in increases in lower extremity muscle power and strength, and improvements in physical performance (expanded SPPB, TUG, and 20-m walk speed) and balance. Even if participants wish to discontinue the supplements, we will still attempt to follow them for outcomes in order to carry out intent-to-treat analysis at 12 months. Characteristics of the participants missing the 12-month follow-up outcomes will be compared to participants without missing data using chi-square tests and t-tests to determine if there are any differences with regard to intervention group, demographic characteristics, and baseline neuromuscular function outcomes. If a particular group exhibits markedly higher drop-out rates, we will attempt to identify baseline covariates that predict attrition. If such covariates can be identified, the analyses of outcome measures may need to be stratified according to these comparisons to decrease bias. We will use a mixed model with an unstructured covariance matrix to model after-treatment neuromuscular function outcomes between the two groups by time, with adjustment for

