For the muscle biopsy subsample (n=16 per group), primary analyses will proceed on the “intent-to-treat” principle in which data from all randomized participants are used in analyses. All participants who complete the 4-month muscle biopsy and on whom the muscle fiber testing can be completed will be included in the analytic sample. Even if participants wish to discontinue the supplements, we will still attempt to follow them for outcomes in order to do the intention-to-treat analysis at 4 months. Characteristics of the participants missing the 4-month follow-up outcomes will be compared to participants without missing data using chi-square tests and t-tests to determine if there are any differences with regard to intervention group, demographic characteristics, baseline physical performance, and baseline muscle fiber testing. Our primary statistical analyses will focus on testing the primary hypotheses that, compared to placebo, vitamin D supplementation will result in changes in skeletal muscle composition and physiology as quantified by: fiber-type composition and size; fiber force, shortening velocity, and power; NCAM+ myofibers; Runx1, Chrn γ , Scn5a, Myh3, Myog, and NCAM1 expression; SC number; VDR expression; and bioenergetic capacity. For our primary outcome of percent type II fibers we will use analysis of covariance (ANCOVA) to model differences in percent of type II fibers between the two groups, with adjustment for the baseline measure, age, gender, and race. Analysis of other continuous measures will also use the ANCOVA model to compare the groups adjusted for age, gender, and race. In secondary analyses, we will examine if the percent of participants who have a relative increase in type II fibers of 25% or more from baseline differs by intervention group using Fisher’s Exact Test, and in logistic regression models adjusted for age, gender, and race. Furthermore, we will explore if the relationship between vitamin D supplementation and neuromuscular function is mediated by change in muscle composition and physiology by including the variables described above as covariates in the ANCOVA model described above. If the relationship between vitamin D supplementation and power decreases by 10% or more, it will be considered evidence of partial mediation.

Human Subjects Protection

Subject Recruitment Methods

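### The gene-expression analysis leaves the 2^-ddCT calibrator, the analysis scale and the baseline covariate open; ANCOVA on log2 -dCT with baseline settles all three at no cost

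*Combined protocol and SAP*

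**What the plan says.** Three places in the combined protocol and SAP bear on this.

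- **Outcome measures, paragraph on Runx1 and its dependent genes.** Expression is "measured by qRT-PCR and normalized to GAPDH expression", so a dCT exists for every sample. CT is then used to calculate 2^-ddCT, "which is needed to compare the gene expression in two different samples". The calibrator sample is not named. The paragraph ends: "Expression of Runx1, Chrny, Scn5a, Myh3, Myog, NCAM1 at baseline and 4-month follow-up will be used in analysis".
- **Statistical Analyses, opening paragraph.** For all continuous outcomes the investigators "will transform them to approximate normality if the outcomes show a strong departure from normality", judged by Q-Q plots and the Shapiro-Wilk test.
- **Statistical Analyses, muscle biopsy subsample.** Percent type II fibers is analysed by ANCOVA "with adjustment for the baseline measure, age, gender, and race". For the rest, including the six genes: "Analysis of other continuous measures will also use the ANCOVA model to compare the groups adjusted for age, gender, and race". Baseline is absent from that second list.

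The genes are among the measures on which the substudy's main analyses focus, but the substudy's primary outcome is percent type II fibers.

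**The concern.** 2^-ddCT has no meaning as an analysis variable until its calibrator is fixed. If the calibrator is each participant's own baseline, every baseline value equals 1 and cannot serve as a covariate, and the analysis becomes a change score on a ratio scale. If the calibrator is common to all samples, the values remain exponentiated and right-skewed unless logged, and whether they are logged depends on a check made once the data are in. Under either calibrator, the covariate list read literally leaves baseline out.

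What is at stake is precision in a comparison of about 32 people, and an analysis scale that is not fixed in advance for any of the six genes.

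**Working it through.** **The plan's own figure.** Statistical Power gives 16 per group for a 25% difference, SD 23.7, two-group t-test, two-sided 0.05. The effect size is 25/23.7 = 1.055. Noncentral-t power is 82.3% at 16 per group and 79.6% at 15, so 16 reproduces; 16/0.9 = 17.8, rounded up to 18. This concerns type II fibers. No power is stated for gene expression.

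**What each calibrator implies.** Let dCT = CT(gene) - CT(GAPDH), and ddCT = dCT(sample) - dCT(calibrator).

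- Own baseline: ddCT at baseline is 0, so 2^0 = 1 for everyone. At 4 months, log2 of the value is -(dCT at 4 months - dCT at baseline), a change score.
- Common calibrator: log2 of the value is -dCT plus a constant, which the intercept absorbs. ANCOVA on the logged value with its logged baseline is therefore identical to ANCOVA on -dCT.

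**Variance on the log scale.** With equal variance at the two visits and correlation rho, the variance factors are 1 - rho^2 for ANCOVA, 2(1 - rho) for a change score and 1 for the 4-month value alone. The documents give no rho for dCT. Their values for other outcomes, both in Statistical Power, serve only as illustration: 0.43 (secondary outcomes, Table 3 footnote) and 0.708 (leg power).

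| | rho 0.43 | rho 0.708 |
|---|---|---|
| Change score vs ANCOVA, 2/(1 + rho) | 2/1.43 = 1.40 | 2/1.708 = 1.17 |
| No baseline vs ANCOVA, 1/(1 - rho^2) | 1/0.815 = 1.23 | 1/0.499 = 2.0 |
| 32 people, change score, worth | 32/1.40 = about 23 | 32/1.17 = about 27 |
| 32 people, no baseline, worth | 32/1.23 = about 26 | 32/2.0 = 16 |

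If the effect is set so that ANCOVA has 80% power, the change score has 66.0% and 73.7% at these two correlations, and the unadjusted 4-month value has 71.7% and 50.9%.

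**Simulation including the raw scale.** All inputs are assumptions: dCT SD 0.25 to 1.5 cycles, rho 0.2 to 0.85, bivariate normal dCT, effect set to 80% analytic power for ANCOVA on -dCT, 16 per group, every model adjusted for age, gender and race. There were 6,000 runs per setting (2,000 for the Shapiro-Wilk rule).

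| Reading of the plan | Power | Points below ANCOVA on -dCT |
|---|---|---|
| ANCOVA on -dCT with baseline | 76-78% | reference |
| Common calibrator, logged, with baseline | identical | 0 |
| Own baseline, logged if Shapiro-Wilk p<0.05 | 54-77% | 1-22 |
| Own baseline, untransformed | 30-76% | 2-47 |
| Common calibrator, untransformed, with baseline | 49-76% | 1-29 |
| Log scale at 4 months, no baseline | 30-78% | 0-46 |

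With the common calibrator untransformed, the loss is about 1 point at SD 0.25, 2-4 at SD 0.5, 12-15 at SD 1.0 and 24-29 at SD 1.5. With baseline omitted on the log scale, the loss is about 0 at rho 0.2, 10 at 0.5, 26 at 0.7 and 46 at 0.85. Type I error was 3.0% to 5.7% throughout.

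**How often the normality check would act.** For own-baseline fold change, Shapiro-Wilk rejected in 10-26% of runs at SD 0.25, 22-72% at SD 0.5 and 63-100% at SD 1.0 or above. At rho 0.5 the own-baseline and common-calibrator values have the same distribution, because 2(1 - 0.5) = 1. There the rates were 18%, 55%, 96% and nearly 100% for SD 0.25, 0.5, 1.0 and 1.5.

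**The case against.** The plan can be read in a way that needs no correction. The clause on 2^-ddCT describes an assay calculation, not a model. The sentence after it uses expression at both visits, which fits poorly with an own-baseline calibrator whose baseline values would all be 1. With a common calibrator, the transformation rule allows a log, ANCOVA is already assigned, and its mention directly after the type II fiber model could be taken to carry the baseline term along. That combination is exactly the analysis recommended here. The transformation rule also tends to act where it matters: the raw scale costs 4 points or less with a common calibrator at SD 0.5 or below, and at SD 1.0 or above the skew is usually detected. Q-Q plots are used as well as the test.

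All of this stands as a reason for restraint. A reader might infer that the plan commits to analysing a raw fold change; it does not, as that is one reading among several. A reader might also infer that ANCOVA on -dCT is clearly more powerful than what is planned. The documents give no dCT SD, correlation or effect and no calibrator, so that cannot be shown. Nor do they support saying that the genes' effects would become non-comparable, since no comparison across genes is planned.

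The objection does not show that the favourable reading is prespecified. It needs three choices that the text leaves open, and on the third the written covariate list points the other way.

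**Conclusion.** The point holds as a gap in specification. Calibrator, scale and baseline covariate are all unsettled for the six genes. No reading examined did better than ANCOVA on -dCT with baseline, beyond simulation error, and several did worse.

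The gain from settling the matter runs from none (common calibrator, logged, baseline-adjusted) to substantial (raw scale with a large SD, change score at low correlation, or baseline omitted at moderate to high correlation). Where the trial falls in that range depends on quantities the documents do not give. The variance ratios of 1.17 to 2.0 borrow correlations from other outcomes, and the simulated figures rest on the stated assumptions.

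The simulations showed no material inflation of type I error. The substudy's primary outcome and sample size are unaffected. This is a free improvement, not a flaw that threatens the trial.

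**What to change.** In the Runx1 paragraph of Outcome measures, and in the biopsy part of Statistical Analyses, state for each of the six genes:

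- The analysis variable is GAPDH-normalised -dCT (log2 scale) at 4 months, fixed in advance and exempt from the data-driven choice of scale.
- The model is ANCOVA with treatment, baseline -dCT, age, gender and race.
- The treatment coefficient is reported as 2^coefficient, the between-arm fold difference, with its confidence limits transformed in the same way.
- 2^-ddCT is used for display only, with its calibrator named.

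The cost is SAP wording. The CT values already planned are sufficient, so no further samples, assays or participants are needed.
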